h Scans performed outside the four-week screening period as standard of care, are acceptable.

i Females of child-bearing age required a negative pregnancy test prior to entering study.

j Follow-up for participants remaining on study was every 6 weeks for the first 3 months, then every 3 months for up to 2 years from completion of therapy. Patients may need to be seen more frequently than these defined intervals based on their medical needs.

In instances where participants discontinued study drug before completion of therapy, they were encouraged to continue with study follow-up visits as long as such procedures did not pose a risk to the well-being of the patient.

Measurement of effect

Survival Measure

At each study visit (every 28 days) while on treatment, patient study status will be collected. If a patient terminates treatment early, the reason and date will be collected. This includes progressive disease, toxicity or adverse event, and death.

Follow-up for participants remaining on study will be every 6 weeks for the first 3 months, then every 3 months for up to 2 years from completion of therapy.

After treatment completion, patient death or lost to follow up will be collected at follow up visits.

Event Measure

Radiographic progressive disease will be captured in the overall response at each disease assessment as per section 9 of protocol. Clinical progression will be documented during study visits as described above.

Full details of the background to the trial and its design are presented in the protocol.

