5. ANALYSIS OF THE PRIMARY OUTCOME(S)

5.1. MAIN ANALYSIS

5.1.1. Event free survival

Primary Estimand

Population: All patients eligible and enrolled into trial with MRT/ATRT (strata 1), osteosarcoma (strata 2), or neuroblastoma (strata 3).

Treatment: Panobinostat

Outcome: Estimated 2-year Event free survival (EFS). EFS is calculated as the time from study enrolment to first documented disease progression, relapse or second malignancy, or death from any cause up to 2 years after study enrolment. The latest possible time of risk being 2 years after enrolment, or the last date known alive.

Summary measure: The probability of EFS (Kaplan-Meier) at with 95%CI will be estimated each stratum*. Kaplan- Meier curves will be plotted for EFS probability, enrolment date as start of risk period. Median EFS time will be calculated at 2 years post-enrolment.

**only calculated if stratum had adequate sample size (osteosarcoma and ATRT/MRT only).*

Subgroup Analysis:

Descriptive statistics (proportions) by subgroup for each disease strata.

Age at enrolment <36 months (3 years old) vs. ≥36 months

Radiation therapy (RT) vs. no RT

Disease status at trial entry (complete response vs stable disease)

Intercurrent Events

Potential intercurrent events:

Patient comes off study or treatment due to toxicity before an event is observed. Patient comes off study or treatment to receive another treatment.

Strategy for handling intercurrent event:

Treatment policy

EFS will be estimated for patients regardless of early treatment or trial termination. This approach assumes that data collected is reflective of those missing data (patients who withdrew from trial).

Sensitivity Analysis

Composite Strategy

Patients coming off study or protocol treatment due to an irreversible or unacceptable dose limiting toxicity or a Serious adverse event (SAE) before an event is observed, will be handled by the composite strategy. The removal from study/treatment date will be treated as an event.

Patients coming off study or protocol treatment to receive another treatment will also be handled by this strategy in the same analysis.

Primary Estimand Calculation

EFS will be estimated and visualised using the Stata sts list and graph commands.

```
stset tvar, fail(event) origin(time enrol_date) enter(time consent_date)
sts list, strata(disease type) risk table(6 12 24) sts graph, strata(disease type) risk
table(0 6 12 18 24) xlabel(0 6 12 18 24) tmax(24) Median EFS will be estimated

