using Stata stsum command stsum, by(disease type)
```

Subgroup analysis

The proportion in each group and 95%CI will be estimated using Stata's *ci proportions* command.

Sensitivity analysis (as above with alternate event) *stset tvar, fail(event_comp) origin(time enrol_date) enter(time consent_date)*

Where time is in months and patients will be censored at their last known contact alive.

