5.1.2. Overall survival

Primary Estimand

Population: All patients eligible and enrolled into trial with MRT/ATRT (strata 1), osteosarcoma (strata 2), or neuroblastoma (strata 3).

Treatment: Panobinostat, dosing as per protocol.

Outcome: Estimated Overall Survival (OS). OS is calculated as the time from study enrolment to death from any cause.

Summary measure: The OS probability (Kaplan-Meier) and 95%CI will be estimated for each stratum* up to 2 years post-enrolment. Kaplan-Meier curves will be plotted for OS probability; enrolment date as start of risk period. The number of deaths and the median OS time will be reported up to 2 years post-enrolment.

**only calculated if stratum had adequate sample size (osteosarcoma and ATRT/MRT only).*

Subgroup Analysis:

As per section 5.1.1

Intercurrent Events

Potential intercurrent events:

Patient comes off study due to toxicity, or to start a new treatment.

Strategy for handling intercurrent event:

Patients coming off study due to a related toxicity or to start a new treatment will be handled with the treatment policy. OS will be analysed for all patients regardless of treatment received until last study visit.

Sensitivity Analysis

Composite Strategy

Patients coming off study due to toxicity or to start a new treatment before death could be observed will be handled by the composite strategy. The removal from study date will be treated as an event/death in sensitivity analysis.

Estimand Calculation

OS will be estimated and visualised using the Stata sts list and graph commands.

stset tvar, fail(death) origin(time enrol_date) enter(time consent_date) sts list,

strata(disease type)

sts graph, strata(disease type) tmax(24)

Median OS will be estimated using Stata stsum command *stsum,*

by(disease type)

Where time is in months and patients will be censored at their last known contact alive.

5.1.3 -Safety

Adverse events will be summarised by grade and type defined by CTCAE Version 4 from 1 week to 12 months after intervention commencement.

Relationship to study drug (definite, probable, possible) adverse events summarised in a table, with the worst AE grade reported by each participant.

A summary table of Dose Limiting Toxicities will include AE type, grade, and frequency.

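### Subgroup EFS and OS are specified as binomial proportions with no rule for patients censored before 24 months, while the stratum figures in the same tables are Kaplan-Meier

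*SAP*

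**What the plan says.** For each stratum, SAP section 5.1.1 says "The probability of EFS (Kaplan-Meier) at with 95%CI will be estimated each stratum", and section 5.1.2 says of OS "The OS probability (Kaplan-Meier) and 95%CI will be estimated for each stratum". Both sections end with the same censoring rule: "Where time is in months and patients will be censored at their last known contact alive".

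The subgroups are age at enrolment below or above 36 months, radiotherapy or none, and complete response or stable disease at entry. For these, section 5.1.1 promises "Descriptive statistics (proportions) by subgroup for each disease strata". Its calculation paragraph adds "The proportion in each group and 95%CI will be estimated using" the Stata command `ci proportions`. For OS, the subgroup paragraph of section 5.1.2 reads only "As per section 5.1.1".

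The shells of Tables 8 and 9 place subgroup cells for a proportion with 95% CI below the stratum EFS or OS estimate. Each table carries a footnote giving the horizon as 2 years from enrolment.

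The SAP expects some patients to leave early. The intercurrent-event text of sections 5.1.1 and 5.1.2 covers patients who come off study before an event or death, and section 5.1.1 mentions patients who withdrew from the trial. Section 2.7 says of patients who stopped the drug early that "they were encouraged to continue with study follow-up visits as long as such procedures did not pose a risk". Section 8 and Table 14 list who was censored and when. None of these places says how such a patient enters a subgroup proportion.

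**The concern.** The `ci proportions` command works on a yes/no variable. A patient last seen event-free at month 3 has no known yes/no status at month 24. To run the command, someone must code that patient as event-free, code the patient as a failure, or leave the patient out. The SAP names none of the three, so the choice would fall to whoever programs the table.

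The same patient needs no such choice in the stratum row above, where Kaplan-Meier uses the follow-up that exists and then censors. One table would then treat one patient under two rules, one of them unstated. If early departures are unevenly spread between, say, younger and older children, the coding alone could create or hide an apparent subgroup difference in a primary endpoint.

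**Working it through.** **Inputs from the SAP.** Stratum sizes are 14 (MRT/ATRT), 9 (osteosarcoma) and 2 (neuroblastoma), from section 2. The horizon is 24 months from enrolment. The SAP gives no event or withdrawal counts, so every count below is an assumption. It also states no figure on this point to reproduce. Its one design figure, the minimum of 14 patients per stratum in section 2.6, is recovered by an exact search (attained alpha 0.148, power 0.903) but plays no part here.

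**Direction of the bias.** Let S be true event-free survival at 24 months, F = 1 − S, and G(u) the probability of not having been censored by time u. Assume withdrawal is independent of prognosis, so that Kaplan-Meier targets S. Let A be the expected share of patients with an observed event, the integral of G dF to 24 months. Since G(24) ≤ G(u) ≤ 1, A lies between G(24)·F and F.

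- Coded event-free: 1 − A ≥ S, upward.
- Dropped: S·G(24) / (S·G(24) + A) ≤ S, downward.
- Coded as failure: S·G(24) ≤ S, downward.
- With nobody censored, G = 1 and all three equal S.

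**A subgroup of 7 (half of 14), assumed data.** Events at months 2, 4 and 6; event-free withdrawals at months 3 and 5; two patients event-free to month 24.

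- Kaplan-Meier: 6/7 × 4/5 × 2/3 = 48/105 = 45.7%
- Coded event-free: 4/7 = 57.1%
- Dropped: 2/5 = 40.0%
- Coded as failure: 2/7 = 28.6%

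**A stratum of 14, assumed data.** Eight events at months 2, 3, 4, 5, 6, 8, 10 and 14, with 0 to 4 event-free withdrawals:

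| Withdrawals (month) | Kaplan-Meier | Coded event-free | Dropped | Coded failure |
|---|---|---|---|---|
| none | 0.429 | 0.429 | 0.429 | 0.429 |
| 7 | 0.402 | 0.429 | 0.385 | 0.357 |
| 4, 7 | 0.359 | 0.429 | 0.333 | 0.286 |
| 3, 7, 12 | 0.334 | 0.429 | 0.273 | 0.214 |
| 1, 4, 7, 12 | 0.266 | 0.429 | 0.200 | 0.143 |

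Subgroup proportions, weighted by their denominators, average to the crude stratum proportion. With two withdrawals that is 6/14 = 0.429 (event-free), 4/12 = 0.333 (dropped) or 4/14 = 0.286 (failure), printed beneath a stratum Kaplan-Meier figure of 0.359.

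**Large samples, exponential event and withdrawal times.** The withdrawal percentage is the probability of withdrawing by 24 months in the absence of events. Each cell shows coded event-free / dropped:

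| True 2-year value | 10% withdrawal | 20% withdrawal | 30% withdrawal |
|---|---|---|---|
| 0.20 | 0.230 / 0.190 | 0.262 / 0.178 | 0.296 / 0.166 |
| 0.40 | 0.426 / 0.385 | 0.453 / 0.369 | 0.482 / 0.351 |
| 0.60 | 0.619 / 0.586 | 0.638 / 0.570 | 0.658 / 0.552 |

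**Sensitivity to one patient.** In a subgroup of 5, recoding one patient between event-free and failure moves the proportion by 1/5, or 20 percentage points.

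**The case against.** A reader might infer that the SAP counts withdrawn patients as successes, or removes them, and that the subgroup figures are therefore certainly biased. The text does not support that. It states no coding, failure is a third possibility, and the bias arises only if someone is censored event-free before 24 months.

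Such censoring may be rare. The last arm closed in December 2021 and the SAP dates from December 2024, so 24 months from enrolment had passed for every patient. Planned follow-up runs to 2 years after the end of therapy, beyond the horizon. Stopping the drug is not itself censoring, because the treatment-policy strategy keeps such patients in the analysis. The section 2.7 wording therefore shows only that later follow-up was not assured. These points limit the likely size, but the SAP still anticipates withdrawal and fixes an estimator that works only without it.

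The SAP also never says what the proportion is a proportion of. It could mean the crude share with an observed event, a legitimate description that need not match Kaplan-Meier. But the cells sit in the EFS and OS tables, with confidence intervals and a 2-year footnote, and will be read as 2-year estimates unless labelled otherwise.

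Finally, precision is poor whichever method is used. In the example of 7, exact 95% intervals are 18–90% for 4/7 and 5–85% for 2/5, and the Kaplan-Meier log-log interval is about 7–80%. Differences of 6 to 11 points are small beside these. That bears on importance; it does not justify using two methods in one table. The per-patient listings will reveal early censoring but supply no rule for it.

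**Conclusion.** The point holds as a conditional one. The estimator specified for subgroup EFS and OS cannot accommodate patients censored before 24 months, and the SAP does not say how to code them. If any exist, the figure read as a 2-year probability is biased, in a direction set by the unstated coding, and need not reconcile with the stratum Kaplan-Meier figure above it. If none exist, the methods coincide.

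In the assumed subgroup of 7, the departure from Kaplan-Meier is +11.4 points (event-free), −5.7 (dropped) or −17.1 (failure). With 20% withdrawal and a true value of 0.40, the large-sample bias is +5.3 points (event-free) or −3.1 (dropped). These sizes rest on assumed counts and on withdrawal unrelated to prognosis, an assumption the SAP's main analysis also makes. The consequence is for descriptive reporting of primary endpoints; no test or decision rule depends on these rows. The change should be made, but the stratum-level results do not depend on it.

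**What to change.** In section 5.1.1, and by reference in 5.1.2, replace the `ci proportions` subgroup line with Kaplan-Meier 2-year EFS and OS with 95% CI for each subgroup within stratum, under the same `stset` as the main analysis. Beside each estimate report n, events and the number censored before 24 months. Where a subgroup is too small, report those counts alone, with no percentage labelled as 2-year EFS or OS. State in advance the size below which this applies. Change the proportion cells of Tables 8 and 9 to match.

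The cost is a few sentences, two table shells and a few lines of Stata. Intervals will be wide, or not estimable, in very small subgroups. With censoring, subgroup Kaplan-Meier values need not average exactly to the stratum value either, but they target the same quantity under the same rule, and the counts let a reader see why they differ.

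### The composite EFS sensitivity code changes only the failure flag and names no composite time, so it does not put the event at the removal date as its text requires

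*SAP*

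**What the plan says.** All of this is in SAP section 5.1.1 unless noted.

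- **Main strategy.** Removals are handled by treatment policy: "EFS will be estimated for patients regardless of early treatment or trial termination".
- **Composite strategy.** Patients who come off study or treatment for a qualifying toxicity or SAE, or to receive another treatment, count as failures: "The removal from study/treatment date will be treated as an event".
- **Main code.** "stset tvar, fail(event) origin(time enrol_date) enter(time consent_date").
- **Composite code.** It is introduced as "Sensitivity analysis (as above with alternate event") and reads "stset tvar, fail(event_comp) origin(time enrol_date) enter(time consent_date").
- **Censoring and time unit.** The sentence after the composite line gives time in months and adds that "patients will be censored at their last known contact alive".
- **Limit on time at risk.** "The latest possible time of risk being 2 years after enrolment, or the last date known alive". In the code, 24 months appears only as a tabulation point and in the graph options, "xlabel(0 6 12 18 24) tmax(24").

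Two other places matter. Section 2.7 says patients who stopped the drug early were encouraged to stay in follow-up. Section 5.1.2 defines a similar composite analysis for OS, with removal from study counted as a death, but gives no code line for it.

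**The concern.** In Stata, `fail()` decides whether a record ends in failure and the time variable decides when. The composite text fixes both: removal is a failure, and it happens on the removal date. The composite code changes only the first. Nothing in the section names a second time variable or tells the programmer to rebuild `tvar`, and the introduction says that only the event alternates.

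Under treatment policy, follow-up is meant to continue past removal, so the main-analysis time can lie well after the removal date.

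This is the only sensitivity analysis stated for EFS, a primary endpoint, and it bears on the SAP's assumption that the observed data represent patients who withdrew. If it returns an unchanged median because of how time was coded, a reader could take that as robustness. With 14 patients in the ATRT/MRT stratum and 9 in osteosarcoma, each patient carries about 7 points (1/14) or 11 points (1/9) of EFS, so a few mistimed removals would show.

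**Working it through.** The SAP states no EFS figure to reproduce, so the check compares code with text and then shows how far the two readings can differ.

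**Step 1. The code lines side by side.** Between the main and composite lines, `event` becomes `event_comp`. `tvar`, `origin` and `enter` are identical.

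**Step 2. What happens to a removed patient** if `tvar` is the main-analysis time:

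| Patient after removal | Main | Composite, as coded | Composite, as written in the text |
|---|---|---|---|
| Later progresses | Fails at progression | Fails at progression | Fails at removal |
| Stays event-free, still followed | Censored at last contact | Fails at last contact | Fails at removal |
| Last contact is the removal date | Censored at removal | Fails at removal | Fails at removal |

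Code and text disagree in the first two rows and agree in the third.

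**Step 3. Worked example, n = 14 (hypothetical data).** In the main analysis, events fall at 1.5, 2, 3, 4, 5, 6, 8, 10, 13, 16 and 20 months, and three patients are event-free at 24. Three patients were removed: one at 2 months (progressed at 10), one at 3 (progressed at 16) and one at 2.5 (event-free at 24). Nobody is censored before 24, so EFS(t) = 1 − (events by t)/14. The median is the first time at which EFS is 50% or less.

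| | 6 months | 12 months | 24 months | Median |
|---|---|---|---|---|
| Main | 8/14 = 57% | 6/14 = 43% | 3/14 = 21% | 8 |
| Code, time cut at 24 | 8/14 = 57% | 6/14 = 43% | 2/14 = 14% | 8 |
| Text | 5/14 = 36% | 4/14 = 29% | 2/14 = 14% | 4 |

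By the text, the first seven failures are at 1.5, 2, 2, 2.5, 3, 3 and 4 months, so EFS reaches 7/14 at month 4. If time is not cut at 24 and the event-free patients are followed further, the code gives 3/14 = 21% at 24 months, the main value.

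**Step 4. Larger illustration (assumed inputs).** Each row is one simulated cohort of 4000 with exponential EFS. A given share is selected for removal, uniformly between 0.5 and 6 months, and is removed only if still event-free. Time is cut at 24 months.

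| Median EFS assumed | Selected | Removed patients lost at removal | 6-month EFS: main / code / text | Median: main / code / text |
|---|---|---|---|---|
| 12 | 10% | none | 71 / 71 / 64% | 12.1 / 12.1 / 10.3 |
| 12 | 20% | none | 70 / 70 / 56% | 11.7 / 11.7 / 7.7 |
| 12 | 30% | none | 71 / 71 / 50% | 11.8 / 11.8 / 5.9 |
| 12 | 20% | half | 71 / 64 / 56% | 12.2 / 10.5 / 8.2 |
| 12 | 20% | all | 70 / 56 / 56% | 11.8 / 8.0 / 8.0 |
| 4 | 20% | none | 34 / 34 / 27% | 4.0 / 4.0 / 3.3 |

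The second row can be checked by formula. By month 6 every selected patient has failed under the text rule, so EFS(t) = (1 − 0.20) × 2^(−t/12) from then on. That gives 0.80 × 0.707 = 57% at 6 months and a median of 12 × log2(1.6) = 8.1 months, against 56% and 7.7 in the simulated cohort.

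**Step 5. The 24-month estimate.** In all these settings code and text agree at month 24. For example, the second row gives 24% main, 19% code and 19% text. The agreement is exact because nobody else is censored before 24, so both codings count the same failures by then. With other early censoring it is only close. If the Step 3 patient with an event at 8 is instead censored at 8, the code gives (8/14) × (3/7) × (2/3) = 16% and the text gives (5/14) × (2/4) = 18%.

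**The case against.** The strongest reply is that `tvar` is never defined. The OS code uses the same name with `fail(death)`, where the time must differ from EFS time, so `tvar` may be a placeholder for whatever time suits the analysis. The text gives the correct date, and an analyst who follows it will build the right variable. This stands to the extent that the documents show a specification at odds with its own rule and do not prove a wrong analysis. It does not remove the point: the flags have separate names, the time does not, and the code is said to differ only in the event.

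A reader might infer that the coded analysis cannot move the 2-year EFS. The documents do not support that. Section 5.1.1 limits time at risk to 2 years. If that limit is applied when `tvar` is derived, event-free removed patients fail at month 24 and the estimate falls much as the text intends. Follow-up after stopping the drug was only encouraged, and the rule also covers patients who leave the study; where last contact is the removal date, code and text coincide.

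A reader might also count the absence of an exit at 2 years and of a month conversion in the `stset` lines as errors. A Kaplan-Meier estimate at 24 months does not use later data, and neither does a median below 24 months. The SAP states that time is in months and section 3.7 gives the conversion. If `tvar` is already in months, adding a scale option would convert it twice.

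**Conclusion.** The point holds as a conflict between the composite rule and the code given for it. Run literally with the main-analysis time, the code leaves the early EFS curve and the median at or near the main result for removed patients who remain in follow-up. In the 12-month setting with 20% selected and all followed, the code misses a fall of about 14 points at 6 months (70% to 56%) and about 4 months in the median (11.7 to 7.7). With half of the removed patients lost at removal the gap is about half as large, and with all of them lost it is nil. The 24-month estimate is materially affected only if time runs past 2 years.

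These sizes rest on assumed removal rates, removal times and median EFS, because the SAP gives none. Severity is minor to moderate: the main EFS and OS estimates are untouched.

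**What to change.** In section 5.1.1, define `tvar_comp` as the earliest of the EFS event date, the qualifying removal date and the censoring date, no later than 2 years after enrolment. Replace the composite line with `stset tvar_comp, fail(event_comp)` and the existing origin and entry options. State in one sentence what `tvar` is in the main EFS analysis.

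In section 5.1.2, give the OS composite analysis its own time in the same way: the earliest of death, qualifying removal from study and censoring.

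Optionally, make the `stset` lines carry the stated 2-year limit and month scale explicitly, after settling whether `tvar` is held as a date or in months. This is tidying and does not correct the 2-year estimate.

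The cost is one derived variable per endpoint and a few lines of SAP text. No new data are needed.
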